8.3 Co-Enrollment Criteria

Participants will be excluded from study participation if they are actively enrolled in a current adherence-related interventional research study.

8.4 Screening for Eligibility

After the patient gives permission to review her/his medical/research records, the study staff member will screen for eligibility by examining the medical records to confirm that the patient initiated ART containing tenofovir within the last 4 months and record the most recent VL value and date of draw.

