4. PROTOCOL SUMMARY

Full Title: An Adherence Feedback Pilot: Integrating DBS Results into Clinic Practice

Title of Main Protocol: Use of ARV Drug Levels in DBS to Assess and Manage ART Adherence in South Africa

Short Title: ADD-ART Protocol – Adherence Feedback Pilot

Sample Size: 60

Study Population: HIV-infected adults who have been on an ART regimen containing tenofovir for at least 4 months.

Participating Sites: Desmond Tutu HIV Foundation Gugulethu Research Offices, Cape Town, South Africa; NY State Psychiatric Institute/RFMH, New York, NY

Study Design: This is a prospective, pilot study of HIV-positive individuals who have been on tenofovir-containing antiretroviral therapy for at least 4 months. The overall goal of this research is to determine the feasibility of giving patients and their providers monthly feedback about Tenofovir-Diphosphate (TFV-DP) drug levels and to examine patient and provider behaviors in response to receiving this information. This study will build upon the Aim 1 observational study and the subsequent patient and provider Feedback Development Workgroups (FDWs).

We will consent a sample (N=60) of HIV-positive patients for monthly assessments, including blood specimen collections to assess TFV-DP drug levels. Participants enrolled in this prospective, pilot study will be randomized to either the intervention arm in which they will receive monthly feedback on their TFV-DP drug levels (Feedback Group; N=30) or the control arm in which they will receive no feedback on TFV-DP drug levels (No Feedback Group; N=30).

The study will take place at the Gugulethu Research Offices (GRO) of the Desmond Tutu HIV Foundation (DTHF) in Gugulethu, 15km outside Cape Town, South Africa (SA). Study participants will be recruited from patients attending one of four public-sector ART clinics in the Klipfontein Health District, Western Cape, including (1) Hannan Crusaid Treatment Centre, (2) Nyanga Clinic, (3) Gugulethu Clinic (NY1), and (4) Vuyani Clinic.

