7. STUDY DESIGN

The study will take place at the Gugulethu Research Offices (GRO) of the Desmond Tutu HIV Foundation (DTHF) in Gugulethu, 15km outside Cape Town, South Africa. Study participants will be recruited from patients attending one of four public-sector ART clinics in the Klipfontein Health District, Western Cape. Recruitment clinics will include (1) Hannan Crusaid Treatment Centre, (2) Nyanga Clinic, (3) Gugulethu Clinic (NY1), and (4) Vuyani Clinic.

We will enroll a sample of (N=60) HIV-positive patients who have been on tenofovir-containing antiretroviral therapy for at least 4 months. Participants enrolled in this prospective, pilot study will be randomized to either the intervention arm and receive monthly feedback on their TFV-DP drug levels (Feedback Group; N=30) or the control group and receive no feedback (No Feedback Group; N=30). After baseline interviews and blood sample collection, all participants will begin using a Wisepill device for four months, return each month to give new blood samples and, for the Feedback Group only, receive feedback on previous month's adherence.

Providers will also be consented into this study which will allow for the review of medical notes made by the providers managing the patients who have enrolled in the trial. Providers of participants in the intervention arm will also simultaneously receive separate monthly messages on patients' TFV-DP drug levels through the clinic systems, and we will monitor subsequent clinical interactions and changes in patient management following this provider feedback. We will conduct participant Exit Interviews and provider FGDs among clinical staff to further understand how both groups did or did not use the feedback and to obtain recommendations for improvements.

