8. STUDY POPULATION

The study will enroll a sample of 60 HIV-positive patients who have been on tenofovir-containing antiretroviral therapy for 4 or more months. Participants enrolled in this prospective, pilot study will be randomized to either the intervention arm and receive monthly feedback on their TFV-DP drug levels (Feedback Group; N=30) or the control group and receive no feedback (No Feedback Group; N=30).

The study will also consent ART providers, inclusive of nursing personnel (Nurse Initiated and Managed ART Therapy-NIMART providers and nursing sisters) and medical officers, at each of the four study clinics.

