8.1 Inclusion/Exclusion Criteria

8.1.1. Patient Participant Inclusion Criteria

Individuals who meet all of the following criteria are eligible for inclusion in the study:

- 18 years of age or older
- HIV-positive
- Initiated ARV's containing tenofovir 4 or more months ago

- Speaks English or Xhosa
- Willing to attend 5 study visits approximately one month apart
- Willing to allow the study team to contact his/her HIV care provider about his/her monthly TFV-DP drug level
- Willing to use Wisepill to dispense ARVs for 4 months
- Willing to receive SMS and/or phone call reminders to charge the Wisepill
- Willing to allow the study team access to their medical chart/clinic folder

Participants will be recruited without regard to gender or race/ethnicity. However, based on clinic profiles, we expect the majority (about 70%) to be women and over 90% to be Black African, with the remainder, if any, of mixed race.

To generate a study sample that closely represents the clinic population, participants will be recruited regardless of VL. Based on clinic profiles, we expect the majority of participants (about 80%) to be virally suppressed based on the last standard of care (SoC) VL with the remainder being unsuppressed. The South African National Health Laboratory Service (N HLS), which assays the VL, currently uses a cut-off of less than 50 copies/mL to denote undetectable VL.

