8.1.3. Patient Participant Exclusion Criteria

Individuals who do not meet inclusion criteria or who meet any of the following criteria will be excluded from the study:

- Unable to provide informed consent
- Unwilling to participate in study procedures
- Unwilling to allow the study team to contact his/her HIV care provider about his/her monthly TFV-DP drug level
- Any condition that, in the opinion of the principal investigator would make participation in the study unsafe, complicated interpretation of study outcome data, or otherwise interfere with achieving the study objectives.

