8.2.2 Recruitment Methods

Patient participants will be invited to participate in the following ways:

- participants from ADD-ART Aim 1 study who provided consent to be contacted about additional research studies will be contacted and offered participation
- Participants on ART will be invited by a research assistant (RA) while in the ART pharmacy waiting room at the four eligible HIV-care facilities.
- Participants on ART will be invited by a research assistant (RA) after finishing in the blood rooms for VL monitoring at the four eligible HIV-care facilities.

Study staff will explain the study verbally in detail, including the purpose of the study, why the patient has been approached by the study staff for participation, and the study procedures (including risks and benefits) and will answer questions to ensure that the patient understands what would be expected of her/him. A patient who remains interested will be told that eligibility will depend on study staff reviewing medical records to confirm age and ART use for at least 4 months and contact her/him if eligible. Potential participants will be told that participation in this study is completely voluntary and their decision whether or not to participate in the study or provide permission for screening will not affect any medical treatment they are receiving at the clinic or their participation in any other studies being conducted by the DTHF.

PI [name] and the study team will recruit providers to take part at the four clinics prior to patient enrollment. Providers will be reminded that participation is completely voluntary and will not affect their employment at any of the four sites. This informed consent will allow for review of their

medical notes of those participants that have enrolled in the trial, and also their participation in the FDGs.

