8.5 Study Enrollment- Patient Participants

If, after reviewing a patient's ART history, the PI/study coordinator (SCO)/MO (with input from study staff) determines that the patient meets study inclusion criteria, study staff will contact the patient by her/his preferred method (phone or in person visit) and, if the patient is still interested, will schedule the Baseline Visit at the Gugulethu Research Offices (GRO) ideally within 1 week but no more than 2 weeks after the initial date of recruitment and clinical/research record review.

If the patient does not meet the inclusion criteria, study staff will contact the patient to tell the patient that s/he is not eligible for the study.

At the Baseline Visit, the participant will provide documented (by signature or witnessed fingerprint) informed consent, be enrolled in the study, complete the baseline assessments, and provide blood samples. All activities related to screening and enrollment will be documented in a designated log.

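### Section 8.4 turns the four-month minimum on tenofovir-containing ART into a maximum, contradicting the inclusion criterion in 8.1.1

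*Combined protocol and SAP*

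**What the plan says.** Six sections of the combined protocol and SAP put a clear direction on the four-month tenofovir or ART requirement.

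- Section 8.4, the screening instruction, has staff examine the records to "confirm that the patient initiated ART containing tenofovir within the last 4 months". The same sentence has them note the latest viral load and its date.
- Section 8.1.1, the formal inclusion criterion, requires ART "containing tenofovir 4 or more months ago".
- Section 4, under study population: "HIV-infected adults who have been on an ART regimen containing tenofovir for at least 4 months".
- Section 7, study design: patients who "have been on tenofovir-containing antiretroviral therapy for at least 4 months".
- Section 8, study population: "tenofovir-containing antiretroviral therapy for 4 or more months".
- Section 8.2.2, which tells patients what the record review is for: to "confirm age and ART use for at least 4 months". Tenofovir is not named here, but the direction is a minimum.

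Two sections govern who is finally in or out. Section 8.1.3 excludes "Individuals who do not meet inclusion criteria". In section 8.5 the PI, study coordinator or medical officer, having reviewed the ART history, "determines that the patient meets study inclusion criteria".

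Two further places touch the subject without settling it. Table 1 lists time on ART among the items to check, with no number or direction. Section 12.6 describes recruits as taking tenofovir-containing ART over the past four months, which can be read either way.

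**The concern.** Section 8.4 is the working instruction for the record check, and it states the opposite of the criterion being checked. A staff member following it to the letter would confirm the wrong fact. The stake is the integrity of screening. An eligible patient could be wrongly turned away, or staff could be unsure which rule to apply. Alternatively, staff follow 8.1.1, as they should, and the correctly enrolled patients do not match the written 8.4 step. Section 8.5 requires screening and enrolment activities to be logged, so a mismatch of that kind could appear in the trial's own records.

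**Working it through.** The plan gives no figure to reproduce here; the check is logical.

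**Inputs.** Let T be the months since tenofovir-containing ART was started.

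- Section 8.1.1 requires T ≥ 4.
- Section 8.4, as written, requires T ≤ 4.

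**Overlap.** Both hold only when T = 4.

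| Time since start | Meets 8.1.1 | Meets 8.4 as written |
|---|---|---|
| T < 4 | no | yes |
| T = 4 | yes | yes |
| T > 4 | yes | no |

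Away from the boundary, the two rules give opposite answers for every patient.

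**Which direction is meant.** The documents answer this themselves.

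1. Five sections (4, 7, 8, 8.1.1 and 8.2.2) state a minimum, and one of them is the formal criterion. Only 8.4 states a maximum.
2. Section 8.4 has staff record the latest viral load, and 8.1.1 expects about 80% of participants to be suppressed on their last standard-of-care result. Section 5.1.2 says such tests typically fall at 4 and 12 months after starting ART, then every 12 months. A patient who started less than 4 months ago would typically have no such result yet.
3. The first recruitment source in 8.2.2 is Aim 1 participants. Section 5.1.4 says they were already on tenofovir at Aim 1 enrolment and then gave 12 monthly samples. Those who completed and are still on tenofovir are well past four months and would fail 8.4 as written.

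**Does anything else in the text cure it?** No other section qualifies or explains the 8.4 wording. Table 1 gives no direction and 12.6 is ambiguous.

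**Does it reach the statistics?** The power statements in 12.1 use 60 participants (30 per arm), three change scores each, an ICC of 0.20 and, for the 5.59-point difference, a standard deviation of 11.42 percentage points. Time on tenofovir enters none of these. The primary analysis model contains a constant and the group indicator only. Nothing there changes.

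**The case against.** The strongest reply is that this is an evident drafting slip that the protocol already guards against. Section 8.4 contains no rejection rule: it asks staff to confirm a fact and record a viral load. The decision is made in 8.5, against the inclusion criteria, and a patient is told of ineligibility only for failing those criteria. Section 8.1.3 ties exclusion to the same list.

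Most of this stands, and it limits the consequence in both directions. A reader might infer that recent starters would be enrolled, or that nearly all eligible patients would be rejected. The documents support neither, because each would need staff to let 8.4 override 8.1.1 despite five consistent sections.

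A reader might also go from the TFV-DP half-life of about 17 days in 5.1.3 to misleadingly low feedback results in patients still accumulating drug. That depends on enrolling patients whom 8.1.1 excludes, and 5.1.3 also reports about 30% variability between people at steady state, which would blur much of such an effect. It is not part of this point.

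The reply does not remove the contradiction. Section 8.4 is the instruction for the check itself, and no reading of its wording agrees with 8.1.1.

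**Conclusion.** The contradiction is certain: 8.4 reverses the inclusion criterion, and the two agree only at about exactly four months. It should be corrected, but it is a modest fault. The realistic harm is confusion or some wrongful rejection at screening, or correctly enrolled patients departing from a written step. That assessment assumes the 8.5 decision is made against 8.1.1, as the text says.

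No count of affected patients is offered. The reversal does not depend on one, and the clinic figures in 8.2.1 do not give the distribution of time on tenofovir across the four clinics.

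Section 12.6 might be taken for a second contradiction. Its wording is ambiguous and can be read consistently with 8.1.1, so it does not count as one. Sample size, power and the analysis model are untouched.

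**What to change.** Reword the 8.4 sentence so that staff verify a tenofovir start at least four months earlier, matching the protocol's own criterion in 8.1.1. Then check that the screening form and the screening and enrolment log do not carry the same reversal. Those forms are not among the documents, so no error in them is assumed.

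Optionally, tidy 12.6 in the same revision so that it also reads as a minimum duration.

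The cost is one sentence and a check of two forms, plus a second sentence if 12.6 is included. Visits, sample size and analysis stay as they are.

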8.5 Study Enrollment- Patient Participants

If, after reviewing a patient's ART history, the PI/study coordinator (SCO)/MO (with input from study staff) determines that the patient meets study inclusion criteria, study staff will contact the patient by her/his preferred method (phone or in person visit) and, if the patient is still interested, will schedule the Baseline Visit at the Gugulethu Research Offices (GRO) ideally within 1 week but no more than 2 weeks after the initial date of recruitment and clinical/research record review.

If the patient does not meet the inclusion criteria, study staff will contact the patient to tell the patient that s/he is not eligible for the study.

At the Baseline Visit, the participant will provide documented (by signature or witnessed fingerprint) informed consent, be enrolled in the study, complete the baseline assessments, and provide blood samples. All activities related to screening and enrollment will be documented in a designated log.

8.6 Participant Retention

Locator information will be collected from each participant at each visit, so that s/he can be found if her/his phone number or address changes. This locator information will be collected and confirmed/updated at each monthly visit. Our study staff will track participants and maintain engagement. SoC is for study staff to send text messages, call or conduct a home visit (with advance permission only) when a patient misses clinic appointments or pharmacy refills. If the participant has given permission, study staff will send text messages reminding her/him of the monthly study appointment, and, if a participant misses an appointment, follow up via call and home visit. A participant missing a study visit will be encouraged to re-schedule the visit within 1 week of the original appointment date (and as close to the target date as possible). A visit will be considered "missed" when 2 weeks have passed since the visit target date. Use of this patient retention strategy in Aim 1 resulted in a retention above 89% across 12 months of follow up.

9. STUDY PROCEDURES/EVALUATIONS

9.1. Provider Consent and Training on Intervention

Prior to the launch of the Aim 2 study, providers will be approached about participating in this study. Consented providers will receive a didactic training from [name] on the meaning and significance of DBS TFV-DP assay results, using protocols developed by the FDW. TFV-DP drug level feedback will then be delivered using these developed protocols.

9.2. Baseline Study Visit (Study Visit 0)

The following procedures/assessments will be performed at the baseline visit:

1. Study staff will obtain **Informed Consent** from the participant.
2. Study staff will complete the **Locator Form**.
3. Study staff will administer the **Baseline Quantitative Assessment**.
4. Study staff will assess **self-reported adherence**.
5. Staff will measure **height and weight**, and assess **pregnancy status** (by self-report, women only).
6. Study staff will obtain blood samples for the following assessments:
 - Dried Blood Spot (DBS)
 - VL (plasma will be stored and tested at patient's end of study)
 - Hematocrit (Hct)
 - Medical record abstraction of most recent Creatinine test
7. Study staff will provide the participant with a **Wisepill device**, instruct the participant on proper Wisepill use (including how to recharge the device) and conduct a Wisepill test (including confirmation that the device is properly connected to the data server).
8. Study staff will document current ARV regimen and dosing schedule(s).
9. Study staff will give the **participant compensation**.
10. Study staff will schedule the next monthly visit.

The baseline procedures/assessments may be conducted over two sessions, with the second session being no more than one week after the initial 0 session. At a minimum, informed consent and locator information will be obtained at the initial Visit 0 session.

9.3. Monthly Follow Up Visits (Study Visits 1-3)

The following procedures/assessments will be performed at every visit:

1. Study staff will verify the patient by the name on the record;
2. Study staff will obtain blood samples for the following: DBS, and 5ml venous blood for VL storage (See Standard Operating Procedure (SOP) C002 BLOOD SPECIMEN ACQUISITION, PROCESSING AND STORAGE GUGULETHU RESEARCH OFFICES (GRO) for additional details);
3. Study staff will assess **self-reported adherence**, measure weight and assess pregnancy status (women only);
4. Study staff will conduct a **Wisepill** device functionality test and will check in with the participant regarding any time(s) participant took a dose without using Wisepill, and resolve any issues;
5. Study staff will update ARV regimen, dosing time(s), and HIV care provider and clinic contact information;
6. In the Feedback arm only: Study staff will use the protocols and materials developed with the FDWs to explain to the participant the results from the previous month's DBS. This will not be an intensive adherence counseling session, but an opportunity to ensure that the participant understands the feedback. If necessary, participants will be referred to an adherence counselor for further support.
7. Study staff will update the **Locator Form**;
8. Study staff will give the **participant compensation**;
9. Study staff will schedule the next month visit.
10. In the Feedback arm only: Providers will receive monthly DBS drug level results for participants randomized to the Feedback study arm, prior to the participant's monthly visit. Results will be shared according to the protocol developed by the FDW.

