9.5. Clinic Chart Review (Visits 1-4 and Post Study)

Study staff will review participants' clinic charts at all visits and post-study to determine if any changes to medical or adherence management were made by providers since the previous visit. These changes could include: additional VL requests (beyond those prescribed for a stable patient), referral for intensive counsellor-based or group adherence counselling (usually only accessed if VL flagged as raised), outreach by Community Care Workers (CCWs) for adherence monitoring and support; and additional doctor-requested patient appointments. To mitigate the risk of control group participants receiving interventional DBS feedback, providers will not receive DBS results for participants in the control group.

The expected quality of the notes in the clinical charts will be variable with some clinicians making detailed notes and others making less detailed notes. The study team is reviewing FDW feedback and considering the creation of a checklist to facilitate identifying and quantifying actions that a provider may take based on DBS results .

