12. STATISTICAL CONSIDERATIONS

12.1. Overview and General Design Issues

For Aim 2, we will explore whether providing adherence feedback to patients and providers results in changes to patient adherence behavior (as measured by TFV-DP levels, VL, Wisepill use patterns, and self-report) and/or provider behavior with respect to patient management (e.g., requests for additional laboratory tests, calling patient back for an additional appointment, referring patient to an adherence counselor, referring patient to the 'risk of treatment failure clinic'). Below we describe the analytical plan to assess change in patient adherence behavior using Wisepill openings as an example.

This 5-month pilot with a small sample size, will provide preliminary estimates that can be used to inform future power calculations and the design of a larger trial (e.g., estimates of effect size, interclass correlation [ICC] for within individual and within provider/clinic correlation). Using Aim 1 data on self-reported adherence, which includes about 3,000 observations, the mean adherence is 81.96% with a standard deviation of 11.42%. The current plan to recruit 60 subjects and collect their monthly adherence data over the subsequent 4-month period will result in 180 change scores (90 per group) for the Aim 2 analysis. Using the estimated standard deviation from our existing data and assuming the ICC between successive change scores is no greater than 0.20, we will be able to detect a 5.59 percentage point difference in ART adherence between the intervention and control group with 80% power. Assume the mean adherence is about 80% for the control group (very close to what we observed from our observational study in Aim 1), if in truth, the mean adherence is 85.59% (which we optimistically believe is achievable), we have 80% probability to declare the difference of adherence between intervention and control is statistically significant. Therefore, we believe that the data we will collect from 60 participants over the 4-months of follow up will provide adequate power to achieve the study goal.

To generate preliminary estimates of the effect of giving feedback on adherence behavior, we will compare change in average percentage of Wisepill openings (for example) from one month to the next between Feedback and No Feedback (Control) participants.

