Because feedback begins at the first return visit at Month 1 after baseline, each Feedback Group participant will provide up to three change score outcomes (for month $i-1$ to month i for $i=2,3,4$). We will compare these to the corresponding change scores in the Control Group in a generalized linear model (GLM) using generalized estimating equations (GEE) to account for within-subject correlation (ICC) among their three change-scores. The analysis model will include a constant term and the group indicator.

With the limited pilot sample size of 60, we will be able to detect moderately large effects on average improvement in adherence. For example, if the ICC between successive change scores is no greater than 0.20, then the detectable standardized mean difference will be $2.8 * [(2/30) * (1 + 0.2 * (3-1))]^{1/2} = 0.86$, a "large" effect.

Given that this is a pilot study, our ability to explore the role of the moderating variables on adherence-related behavior will be limited. However, looking at the monthly change-scores can reveal important features on which to focus. Moreover, the larger Aim 1 sample (N=250) will provide key data on individual and structural factors affecting adherence, retention, and preferences for sample collection and feedback that we will utilize in multivariable analyses as predictors of DBS TFV-DP levels and Wisepill use patterns. We will also examine these factors as potential effect modifiers in Aim 1 analyses.

For providers we will examine changes in clinical management patterns, for example requests for additional tests or adherence counselling sessions usually only triggered by a raised VL.

Similar to Aim 1, the Baseline and Visit 4 (last visit) Quantitative Assessments will cover a large array of participant information and behaviors that could be potential confounders. To examine how potential confounding factors can influence our statistical analysis, we will first identify a list of variables that is possible be candidates for potential confounding factors and then test whether any of those variables is associated with our outcome (i.e., adherence) and exposure (i.e., the intervention) in our sample. If found, we will include them in the primary analysis model to obtain the adjusted intervention effect. While the official primary analysis will be the one without covariate adjustment, the adjusted analysis will help to interpret the findings from primary analysis.

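### Study-staff counselling referrals, a Feedback-arm step only, can be misclassified as provider responses because the plan does not record who initiated a referral

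*Combined protocol and SAP*

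**What the plan says.** Section 9.3, item 6, sets out the feedback step: "In the Feedback arm only: Study staff will use the protocols and materials developed with the FDWs to explain to the participant the results". The item ends with the referral sentence: "If necessary, participants will be referred to an adherence counselor for further support". No threshold for a referral is given, and the control arm has no matching step. Provider feedback is a separate item (item 10).

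Section 9.5 has study staff review clinic charts at Visits 1-4 and after the study "to determine if any changes to medical or adherence management were made by providers since the previous visit". One of its four examples of such a change is "referral for intensive counsellor-based or group adherence counselling (usually only accessed if VL flagged as raised". It also warns: "The expected quality of the notes in the clinical charts will be variable". A checklist of provider actions is under consideration but not adopted.

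Section 12.1 gives as examples of provider behaviour "calling patient back for an additional appointment, referring patient to an adherence counselor, referring patient to the 'risk of treatment failure clinic", and describes the provider analysis as looking at changes in management such as "requests for additional tests or adherence counselling sessions usually only triggered by a raised VL". Clinical management of patients is part of primary objective (b) in section 6.1.

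**The concern.** One kind of action, referral to an adherence counsellor, has two roles. It is something study staff may do as part of the intervention in one arm, and it is something the trial counts as evidence that providers responded to drug-level results. If the two cannot be told apart in the chart, part of the intervention can be read as its own effect.

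Any such error has a clear direction. The staff step exists only in the Feedback arm, so misclassified entries add to that arm's count alone. Section 9.5 says this kind of counselling is usually accessed only when viral load has been flagged as raised, so background counts may be low and a few extra entries could weigh heavily with 30 participants per arm. The pilot is also meant to supply estimates for a larger trial (12.1), and a misattributed provider effect would carry into that design. If the initiator is not recorded at the time, it may not be recoverable from the charts.

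**Working it through.** The plan states no referral rate, effect size or power for provider behaviour, so there is no figure of its own to reproduce. The check is a comparison of sections, followed by an illustration of scale.

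**Comparison of sections**

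| Question | What the plan provides |
|---|---|
| Who makes the referral in 9.3, item 6? | The sentence is passive, but study staff are the only actor named in the item |
| Which arm? | Feedback only |
| Is the same kind of action a provider outcome? | Yes: the chart-review list in 9.5 and the examples in 12.1 ("calling patient back for an additional appointment, referring patient to an adherence counselor") |
| Is the outcome meant to be provider-initiated? | Yes: 9.5 and 12.1 both refer to providers |
| Is there a rule for recording the initiator? | None in 9.3, 9.5 or 12.1, and no item in the schedule of events (Table 1) |
| Can the chart be expected to show it? | Not reliably: 9.5 expects variable notes |
| Are the chart reviewers blinded to arm? | No such provision; 12.4 says the study is not blinded |

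The intended outcome is therefore clear, but the means of measuring it as intended is missing. Misclassification needs two further things: the staff referral, or the counselling that follows it, must be entered in the clinic chart, and the entry must not show who initiated it. The documents neither say that this will happen nor prevent it.

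**Illustration of scale (p and q are assumed)**

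Let p be the provider referral rate, the same in both arms, so that there is no true provider effect. Let q be the share of Feedback participants whose staff referral reaches the chart and is counted as a provider action. If the two occur independently:

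- recorded Feedback rate = p + (1 − p)q
- recorded control rate = p
- spurious difference = (1 − p)q

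With 30 per arm (12.4):

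| p | q | Feedback rate | Spurious difference | Extra participants (30 × difference) | Share of trials with Fisher p ≤ 0.05 |
|---|---|---|---|---|---|
| 5% | 0% | 5.0% | 0 | 0 | 0.1% |
| 5% | 10% | 14.5% | 9.5 points | 2.9 | 8% |
| 5% | 20% | 24.0% | 19.0 points | 5.7 | 40% |
| 5% | 30% | 33.5% | 28.5 points | 8.6 | 75% |
| 10% | 0% | 10.0% | 0 | 0 | 0.9% |
| 10% | 10% | 19.0% | 9.0 points | 2.7 | 8% |
| 10% | 20% | 28.0% | 18.0 points | 5.4 | 30% |
| 10% | 30% | 37.0% | 27.0 points | 8.1 | 61% |

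The last column uses a two-sided Fisher exact test only as a yardstick; the plan specifies no test for provider behaviour. Independence is also an assumption. Staff and providers react to the same drug-level result, so their referrals may fall on the same people. If they overlap as far as possible, the spurious difference falls from (1 − p)q to q − p: for p = 5% and q = 20%, from 19 to 15 points.

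**The case against.** The strongest reply is that the outcome is already defined correctly. Section 9.5 looks for changes made by providers and 12.1 speaks of provider behaviour, so on the text a staff referral is not part of the outcome. This stands. A reader might infer that the plan counts staff referrals as provider behaviour, and the documents do not support that. What remains is a risk of misclassification, because the definition comes with no rule for applying it.

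Second, no section says that a staff referral will be written in the clinic chart. This also stands, and the bias is conditional on it.

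Third, the actions may differ: 9.5 names intensive counsellor-based or group counselling, while 9.3 names a counsellor for further support. The wording in 12.1 is close to that in 9.3, however, and a brief chart note may not show the difference.

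Fourth, other sources bear on attribution. Study staff both give the feedback and review the charts, visit checklists exist (13.5), exit interviews ask about influence from staff and from providers (9.7.3), and provider focus groups ask what providers changed (9.6). These help, but none is planned as a way to classify individual referrals, and the focus groups take place after all participants have finished.

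Fifth, it is tempting to put a number on the bias by taking the roughly 20% expected to be unsuppressed (8.1.1), or 0.20 × 30 = 6 Feedback participants, and comparing 6/30 with 0/30 (Fisher p = 0.024). The documents do not support this. Staff act on drug level, not viral load. Unsuppressed controls are the patients most likely to be referred under standard care, so zero is implausible. The result is also fragile: 5/30 vs 0/30 gives p = 0.052, and 6/30 vs 1/30 gives p = 0.10.

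**Conclusion.** The point holds as a gap in measurement. A counselling referral can come from study staff in the Feedback arm only and is also a provider outcome, and the plan has no means of recording which it was. Any misclassification runs towards a provider effect.

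Its reach is limited. Counselling is one of four example actions in 9.5; the other three (extra viral load requests, outreach by community care workers, additional doctor-requested appointments) are not shown to be affected. The listed components of the primary endpoint in 12.2.1 do not name chart-counted actions, although objective (b) covers clinical management. A reader might infer that the whole provider comparison is compromised; the documents do not show that.

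The size is unknown. The 9.0 to 28.5 points in the illustration rest on assumed rates (p of 5% or 10%, q of 10% to 30%), on independence of the two kinds of referral, and on every referral in q being charted and misread. If staff referrals do not reach the chart, or the notes identify who made them, the bias is zero. The gap is worth closing because the error would favour one arm, may not be recoverable afterwards, and is cheap to prevent.

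**What to change.** Before enrolment:

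- **9.3 and 13.5:** on the existing visit checklist, log every study-initiated referral in either arm, with PID, date and destination.
- **9.5:** for each counselling entry in the chart, abstract the initiator as provider, study staff or unclear, using the log.
- **12.1:** define the provider outcome as provider-initiated actions. Report the counselling count with and without staff-matched or unclear entries. Report staff referrals separately, as part of what the Feedback intervention delivered.

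Do not automatically exclude a provider referral because it follows a staff referral. Under item 10 of 9.3, providers receive the result before the monthly visit, so both may respond to the same result in the same participant. Automatic exclusion would remove genuine provider responses, essentially in the Feedback arm alone, and so bias the comparison the other way.

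The cost is one checklist field, one abstraction rule and slightly more abstraction work. Some entries will remain unclear, which is why the count is reported both ways. Participants' care does not change.
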